7.2 Patient Profiles

In order to assess if safety events affect the efficacy outcomes, patient profiles will also be created. Patient profiles will include a short report for each participant, showing the participant's demographics and baseline information, randomization arm, ocular medications administered during the study, number of cells injected, solicited and non-solicited adverse events, and a few key measures of treatment effect (e.g., visual acuity, OCT, microperimetry). These profiles will exemplify the changes over time to feasibility and whether it correlates with safety events.

7.3 Secondary Efficacy Outcomes

Availability of the secondary outcomes will first be summarized by treatment arm and visit. Due to each secondary outcome having numerous measures associated with it (e.g., the OCT outcome can be measured by looking at macular thickness (central, pericentral and/or peripheral), macular volume, average macular thickness, presence of CME and/or subretinal fluid, integrity of photoreceptor layer, etc.), outcome measures thought to be of most importance were chosen by the Study Chair prior to any knowledge of treatment assignment. Using this pre-selected list of outcome measures, the following strategy will be used to analyze each continuous outcome.

- 1. Summary table of **descriptive** statistics broken down by treatment arm, Treatment Period and visit for change from baseline in the outcome measure. For VA and microperimetry, the summary table will also include the outcome measure on the original scale.
- 2. Analysis of **treatment effect** of cellular vs sham therapy during Treatment Period 1 (as described in Section 7.3.1.1) for the outcome measure on the original scale and change from baseline.
- 3. Analysis of **effect of cellular treatment over time** (as described in Section 7.3.1.2) for the outcome measure on the original scale and change from baseline.

For those outcomes that are categorical, a summary table of counts and frequencies will be provided, with any other planned analyses described within the relevant section.

These analyses will be conducted to gauge any changes in the outcome measures that could be attributed to the cellular therapy and to differentiate these changes from non-treatment factors (i.e., natural course of the condition, learning or placebo effects or testing variations). Graphical measures will be used to summarize and display trends over time. A (modified) intent-to-treat approach will be followed in which all participants who were randomized *and received the first injection* (cellular or sham) will be included in the analysis and analyzed in the arm to which they were randomized.

Based on the observations of the preliminary phase 1 clinical trial, we anticipate any improvement in visual function associated with study cell therapy to occur within 3 months of cell therapy and for any effect to be sustained over time (but not increasing over time).⁵ Due to small sample sizes, it is recognized that there is limited power to detect differences (Appendix), but trends may be identified that would encourage future trials of this treatment, provided no safety concerns are found. Significance testing will use 2-sided tests with alpha=0.05. No adjustment for multiple comparisons will be made as these are purely exploratory analyses for hypothesis generation.

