7.8.2.2 Efficacy

All secondary outcome analyses will follow a similar form and strategy as outlined in the SAP. Data from the study eye will be presented. Tables and graphs of each outcome and change from baseline in each outcome will accompany the results of the analyses as appropriate and will be used to visualize the trends over time. See Section 6.3.2 for a list of outcomes of interest. A (modified) intent-to-treat approach will be followed in which all participants who were randomized *and received the first injection* (cellular or sham) will be included in the analysis and analyzed in the arm to which they were randomized.

The primary analysis will be a comparison at 6 months between those who receive immediate cellular therapy vs those who receive immediate sham therapy. A t-test will be used for continuous outcomes and Fisher's exact test or an appropriate non-parametric test may be used for categorical outcomes. Comparisons at other time points prior to 6 months may also be performed.

An additional analysis will look at treatment effect duration for those who receive immediate cellular therapy and assess whether the treatment effect remains the same at 6 and 12 months or increases/decreases as time passes.

As noted in Section 6.3.2, there are many outcomes of interest within each modality. P-values calculated from the statistical tests noted above will only be used as an indication of strength of association and should not be used for hypothesis testing.

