3.2 Sample Size Considerations

There is no formal sample size calculation for this small phase I/II study and no formal hypothesis testing will be performed. A sample size of 20 participants was chosen to ensure that it is financially feasible to conduct the study and logistically possible to complete the study enrollment within the study period. The primary objective is to assess the safety and feasibility of the stem cell therapy; however, it is desired to obtain some gauge of potential efficacy of this cell therapy. Thus, participants will be randomized 1:1 to immediate cellular therapy/deferred sham or immediate sham/deferred cellular therapy. After their first treatment (cellular or sham), participants will be followed for 6 months, at which time participants who initially received sham treatment will be given stem cell treatment and vice versa. The small sample size is not ideal, but for practical purposes, it would be difficult to increase the sample size significantly without increasing the enrollment period for the study.

Although the study as designed may not be large enough to determine efficacy, some efficacy signals might be observed with the current study design. Such a signal may warrant further investigation of this therapy for CRVO. When a phase II/III randomized controlled trial is planned, appropriate sample size calculations will be performed.

It is recognized that the study has limited power to show efficacy; however, we hope to obtain some trends in change in visual function or retinal morphology or perfusion that may suggest efficacy to justify a larger randomized prospective clinical trial. Power calculations are explored in section 5.2.2 for the proposed method of analyzing the secondary outcomes.

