7.3.1 Secondary Efficacy Outcome Analysis Methods

7.3.1.1 Treatment Effect of Cellular vs Sham Therapy During Treatment Period 1

Comparisons between the two treatment arms will be performed at 1, 3, and 6 months after the first treatment is administered as a method of exploring the differences between cellular and sham therapies. An independent t-test will be used to analyze the treatment effect for each continuous outcome measure on the original scale and change from baseline.

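### The SAP applies a 0.05 significance threshold that the protocol disclaims, and it does not keep month 6 as the primary efficacy comparison

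*SAP*

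**What the plan says.** **Rule for p-values.** Protocol 7.8.2.2 (Efficacy) notes the many outcomes within each modality and says that p-values "will only be used as an indication of strength of association and should not be used for hypothesis testing". SAP 3.2 says that "no formal hypothesis testing will be performed". SAP 7.3 sets a threshold: "Significance testing will use 2-sided tests with alpha=0.05". The sentence after it reads: "No adjustment for multiple comparisons will be made as these are purely exploratory analyses for hypothesis generation". SAP 7.3.1.2 compares the arms on the effect of cellular therapy. If no statistically significant difference is found, the arms are combined for a paired t-test; otherwise each arm is tested separately.

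**Time point.** Protocol 7.8.2.2 says: "The primary analysis will be a comparison at 6 months" (immediate cellular versus immediate sham). Earlier comparisons are optional there. SAP 7.3.1.1 says: "Comparisons between the two treatment arms will be performed at 1, 3, and 6 months after the first treatment is administered". It applies an independent t-test to each continuous measure, both on the original scale and as change from baseline, and ranks none of these tests.

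**Choice of measures.** SAP 7.3 says the Study Chair pre-selected the most important measures before any knowledge of treatment assignment. That list is not ranked.

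**The concern.** The report's author is given two rules. Under the protocol a p-value describes strength of association and decides nothing. Under SAP 7.3 it is judged against 0.05, and under 7.3.1.2 that judgement determines which analysis is run.

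The protocol also gives the reader one time point to look at first, and the SAP does not carry that forward. With three visits, two scales and 31 measures on an equal footing, the plan does not say which result bears most on efficacy.

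Both documents hope for trends that would justify a larger randomised trial. If that reading is made at 0.05 across an unranked set of tests, several nominally significant results are to be expected by chance, and nothing in the SAP tells the reader how many.

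**Working it through.** **1. The plan's own figure.** SAP 13.1 says power does not approach 70% until the difference is about 20 letters. Inputs: 20 participants at 1:1, so 10 per arm; patient-level SD 15; measurement-error SD 6.2; two-sided 0.05.

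- Raw score: SD = √(15² + 6.2²) = 16.23. Noncentrality at 20 letters = 20 / (16.23 × √(2/10)) = 2.76 on 18 df, giving power 0.741. Power of 70% is reached at 19.1 letters. This agrees with the SAP's rounded statement.
- Change from baseline: the patient effect cancels, so SD = 6.2 × √2 = 8.77 and power at 20 letters is 0.998.

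The 13.1 figure therefore describes the raw letter score and not the change score.

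**2. Number of tests.** Continuous measures marked for the treatment-effect analysis in SAP Tables 3 to 9:

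| Modality | Measures |
|---|---|
| Visual acuity | 1 |
| Microperimetry | 2 |
| OCT | 2 |
| OCTA (foveal avascular zone 1; vascular density 3 regions × 2 plexuses = 6; disc and nerve-fibre measures 4) | 11 |
| Multifocal ERG | 4 |
| Full-field ERG | 5 |
| Autofluorescence | 2 |
| Fluorescein angiography | 4 |
| **Total** | **31** |

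Autofluorescence and angiography (6 measures) are not scheduled at month 1 (Protocol Table 2). The count is 25 × 3 visits × 2 scales + 6 × 2 visits × 2 scales = 150 + 24 = **174**.

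Other readings:

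- All 31 measures at all three visits, as SAP Tables 8 and 9 literally state: 31 × 3 × 2 = 186.
- Superficial and deep density counted together: 22 × 6 + 24 = 156.
- Original scale for visual acuity and microperimetry only, since Tables 5 to 9 list only change from baseline: 25 × 3 + 6 × 2 + 3 × 3 = 96.

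These counts cover the Period 1 between-arm tests only. On the change scale, SAP 7.3.1.2 adds 87 between-arm tests, at least 87 paired tests and 31 tests at 12 months.

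**3. Expected chance results.** Number of tests × 0.05, which holds whatever the correlation: 174 × 0.05 = **8.7**; 96 × 0.05 = 4.8; 186 × 0.05 = 9.3. Half of these (4.35 of 8.7) would favour cells.

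**4. Chance of at least one.** If the tests were independent, 1 − 0.95¹⁷⁴ = 0.9999. They are not: they share 20 eyes, repeated visits and two scales of the same data. I simulated 174 tests under no effect with 10 per arm and the 13.1 variance components. An assumed between-measure correlation ρ was applied to both the patient effect and the measurement error.

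| ρ | Chance of at least one p<0.05, all 174 tests | Same, month-6 change only (31 tests) |
|---|---|---|
| 0 | over 99% | about 79% |
| 0.3 | 99% | about 68% |
| 0.5 | about 95% | about 53% |
| 0.7 | 84% | about 36% |
| 0.8 | about 72% | about 27% |
| 0.9 | about 57% | about 18% |

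The placement of the correlation matters. If only the patient effects are correlated, the effect cancels in change from baseline, change-scale tests of different measures stay independent, and the chance remains about 99% even at ρ = 0.9. At high ρ in both components the mean stays near 8.7 but the median falls to 1, because chance results then arrive in clusters.

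**5. What restoring month 6 does.** Month 6 on one scale is 31 tests, with 31 × 0.05 = 1.55 expected by chance. This is a large reduction, but it does not remove the need to say how p-values are read.

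**The case against.** The strongest defence is that the SAP is candid. Its next sentence after the threshold declares the analyses exploratory and unadjusted, the limited power is acknowledged, and efficacy is secondary to safety and feasibility. The measures were pre-selected before any knowledge of assignment. SAP 3.2 denies only formal testing, which can coexist with descriptive p-values. All of this stands, and it is why no multiplicity correction is asked for. It does not reconcile SAP 7.3 with the protocol's wording, which has no such qualifier, and it does not explain why significance decides pooling in 7.3.1.2.

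Three stronger readings are tempting, and the documents do not support them.

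- **That the SAP drops the month-6 comparison.** It does not. Month 6 is tested in 7.3.1.1 and listed in the tables; only its primary status is missing. The protocol itself permits earlier comparisons.
- **That a false efficacy signal is nearly certain.** That requires low to moderate correlation between measures, or correlation confined to the patient effects. The documents give no such correlation, and under strong correlation in both components the chance falls to about 57%.
- **That any single p<0.05 counts as a signal.** Neither document says so. The SAP speaks of trends and gives no numerical rule.

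**Conclusion.** The point holds as a conflict between the documents, with a practical consequence for how efficacy results are read. SAP 7.3 and 7.3.1.2 use a significance threshold for outcomes where the protocol says p-values "should not be used for hypothesis testing", and SAP 7.3.1.1 does not keep the protocol's primary time point.

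The firmest figure is the expected count: about 8.7 nominally significant Period 1 results if the therapy does nothing, or 4.8 to 9.3 depending on how the tables are read. It assumes that each t-test has its nominal 5% level and does not depend on correlation. The chance of at least one, about 57% to over 99%, rests on an assumed ρ from 0 to 0.9 and on applying the visual-acuity variance components to every measure.

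This should be corrected, but it does not threaten the primary safety and feasibility objective.

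**What to change.** 1. **SAP 7.3:** replace the alpha sentence with the protocol's statement on p-values, and report each between-arm difference with a 95% confidence interval.
2. **SAP 7.3.1.1:** name month 6 as the primary efficacy time point, with months 1 and 3 supportive.
3. **SAP 7.3.1.2:** reword so that pooling does not depend on a significance test, for example by always showing by-arm and pooled estimates with intervals. Without this, removing alpha would leave the pooling rule with no threshold.
4. **Reporting:** state the number of tests run and the number of nominal p<0.05 expected by chance, as context for any small p-value.

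No multiplicity adjustment is needed. Naming a lead measure is optional in an exploratory trial. If visual acuity is named, note that the power in SAP 13.1 applies to the raw letter score and not to change from baseline.

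The cost is SAP wording only, with no new data, visits or participants. The downside is that early time points and isolated small p-values will carry less weight in the report.

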7.3.1 Secondary Efficacy Outcome Analysis Methods

7.3.1.1 Treatment Effect of Cellular vs Sham Therapy During Treatment Period 1

Comparisons between the two treatment arms will be performed at 1, 3, and 6 months after the first treatment is administered as a method of exploring the differences between cellular and sham therapies. An independent t-test will be used to analyze the treatment effect for each continuous outcome measure on the original scale and change from baseline.

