3.3 Randomization

Randomization will occur after informed consent has been obtained and once a participant is confirmed to be eligible. Randomization will need to occur prior to the baseline visit for logistical and scheduling reasons. Much coordination among the hematologist, the Good Manufacturing Practices (GMP) facility, and the treating ophthalmologist needs to occur on days in which the cellular therapy is given. Therefore, knowing which treatment arm to which the participant has been randomized prior to the baseline visit is necessary. Great care will be taken to choose participants who are highly motivated to participate so as to prevent drop-out post-randomization.

A secure, internet-based eligibility, enrollment, and randomization system is integrated into the study to control and document the randomization assignments. Eligible participants will be randomized in a 1:1 ratio to immediate cellular therapy/deferred sham therapy or immediate

sham/deferred cellular therapy. Random assignments are generated and maintained by the Data Coordinating Center (DCC).

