13.0 APPENDIX

13.1 Simulation Results

Simulations were used to produce power curves for the independent t-test. The following plots show the power curves for using the t-test in different scenarios with varying degrees of treatment decay and period effect in the simulated data. Treatment decay is defined as the attenuation of cellular treatment, which might be observed in the immediate cellular therapy/deferred sham therapy group during Study Period 2. Period effect is defined as the effect on treatment of being in Study Period 1 versus being in Study Period 2. Estimates of participant level random effects and measurement error used in these power calculations were derived from visual acuity data in the Study of Comparative Treatments for Retinal Vein Occlusion 2 (SCORE 2)⁷.

FIGURE 1 shows the power curve when estimating treatment effect of visual acuity (i.e., difference in number of letters read) holding treatment decay and period effect at 0.

Figure 1: Power Curve for T-test

Standard deviation of the patient level random effect=15 Standard deviation of the measurement error=6.2 Treatment decay (Q)=0 Period effect (T)=0 **FIGURE 2** and **FIGURE 3** show the power of estimating treatment effect of visual acuity while introducing treatment decay and a period effect, respectively.

Figure 2: Power Curve with Differing Levels of Treatment Decay

Figure 3: Power Curve with Differing Levels of Period Effect

Figures 2 and 3 show that treatment decay and a period effect do not affect power. The overall conclusion is that power to detect a treatment effect does not approach even 70% until the treatment effect is quite large (difference of 20 letters read).

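### The SAP expects a visual effect by month 3 that then holds, but compares the arms one visit at a time; averaging months 3 and 6 would cut the variance of change from baseline in acuity by up to a quarter.

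*SAP*

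**What the plan says.** SAP 7.3 draws on the phase 1 experience. It expects any improvement in visual function within 3 months of cell therapy, and it expects "for any effect to be sustained over time (but not increasing over time".

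SAP 7.3.1.1 sets out the between-arm analysis for Treatment Period 1: "Comparisons between the two treatment arms will be performed at 1, 3, and 6 months after the first treatment is administered". Each comparison is an independent t-test, done both on the score itself (the SAP's original scale) and on change from baseline. SAP 7.3 adds: "Significance testing will use 2-sided tests with alpha=0.05". It makes no multiplicity adjustment and calls the analyses exploratory. Neither section plans a contrast that averages visits or a repeated-measures model.

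Protocol 7.8.2.2 ranks the visits. The 6-month comparison is the primary efficacy analysis, and earlier comparisons are optional.

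SAP 13.1 gives the acuity inputs for the power curves: "Standard deviation of the patient level random effect=15 Standard deviation of the measurement error=6.2 Treatment decay (Q)=0 Period effect (T)=0". From its simulations it reports: "power to detect a treatment effect does not approach even 70% until the treatment effect is quite large (difference of 20 letters read". Protocol Table 2 schedules acuity, microperimetry and ERG at months 1, 3 and 6 after each treatment.

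**The concern.** If the effect is present by month 3 and flat thereafter, the month 3 and month 6 arm differences are two noisy readings of one quantity. Testing them separately leaves each estimate with the full error of a single follow-up visit.

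Precision matters here because the sample was set by resources: "A sample size of 20 participants was chosen to ensure that it is financially feasible". SAP 3.2 says it would be hard to enlarge without a longer enrollment period, and the efficacy aim is only to see whether a trend justifies a larger trial. A narrower interval from readings already scheduled serves that aim. Separate tests at 0.05 can also disagree with each other without any real difference between the visits.

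**Working it through.** **Inputs.**
- 20 participants (SAP 3.2), allocated 1:1 (SAP 3.3), taken as 10 per arm.
- Two-sided 0.05 (SAP 7.3).
- Patient SD 15 and measurement-error SD 6.2 letters (SAP 13.1); 6.2² = 38.44 and 15² = 225.
- Assumptions of this check: no missing visits, and an equal effect at months 3 and 6. The 10-letter effect used below is illustrative. The only mean difference that SAP 13.1 discusses is 20 letters.

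**The plan's own figure.** For one visit on the raw score, variance = 225 + 38.44 = 263.44 and SD = 16.23. Noncentral t power with 10 per arm is 49.8% at 15 letters and 74.1% at 20 letters, and it reaches 70% at 19.1 letters. This agrees with the SAP's statement. For one-visit change from baseline, power at 20 letters is 99.8%, so the SAP's statement describes the raw score only.

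**Formulas.** With k follow-up visits averaged and independent visit errors:
- change from baseline: variance = 38.44 × (1 + 1/k)
- raw score: variance = 225 + 38.44/k
- 95% CI half-width = t(0.975, 18) × SD × √(2/10), with t = 2.101

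| Scale | Visits used | Variance | SD | Half-width (letters) | Power at 10 letters | Power at 20 letters |
|---|---|---|---|---|---|---|
| Change | one | 76.88 | 8.77 | 8.2 | 67.5% | 99.8% |
| Change | mean of 3 and 6 | 57.66 | 7.59 | 7.1 | 79.5% | about 100% |
| Raw | one | 263.44 | 16.23 | 15.2 | 25.6% | 74.1% |
| Raw | mean of 3 and 6 | 244.22 | 15.63 | 14.7 | 27.3% | 77.2% |

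Variance cut on change: 1 − 57.66/76.88 = 25.0%. On the raw score: 1 − 244.22/263.44 = 7.3%, because the patient component of 225 does not average out. A simulation of 40,000 trials gave matching power.

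**With baseline as a covariate.** Residual variance = 225 + 38.44/k − 225²/263.44. This is 71.27 for one visit and 52.05 for the average, a cut of 27%.

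**When the best case fails (assumed ranges, change from baseline).**
- *Month 3 and 6 errors correlate at r, both independent of baseline.* Averaged variance = 38.44 × (1 + (1 + r)/2). At r = 0.2 it is 61.50 (cut 20%, power at 10 letters 76.9%). At r = 0.5 it is 67.27 (cut 12.5%, power 73.2%).
- *True change varies between patients, with SD s, the same at both visits.* Add s² to both variances. At s = 5: 101.88 to 82.66 (cut 19%, power 55% to 64%). At s = 10: 176.88 to 157.66 (cut 11%, power 36% to 39%).
- *Error correlation decays with time, 0.2 to 0.4 per 3 months.* The cut is 29% to 32% against month 6 alone, but 15% to 5% against month 3 alone.

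**When averaging loses to month 6.** Let f be the month 3 effect as a fraction of the month 6 effect. The average has the larger standardized effect when (1 + f)/2 > √0.75, so f > 2√0.75 − 1 = 0.73. On the raw score the threshold is 2√0.927 − 1 = 0.93.

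**The case against.** The strongest reply is that this is an optional gain in efficiency, not an error. Efficacy is secondary, SAP 3.2 rules out formal hypothesis testing, and Protocol 7.8.2.2 treats p-values only as an indication of strength of association. The protocol already puts month 6 first, and visit-level results serve the planned display of trends over time. The larger gain, from raw score to change (263.44 to 76.88), is already in the plan. The best-case benefit is about 1.1 letters of half-width. All of this stands, and it limits the point to a supplementary analysis.

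The 25% is also conditional. The 6.2 comes from another trial's data, and the SAP's two-component model allows no patient-specific true change. Protocol 7.4 permits anti-VEGF treatment during follow-up, so such variation is plausible. This objection stands too, and is why the smaller cuts belong beside the 25%.

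A reader might infer more than the documents support:
- *That acuity variance falls by a quarter whatever the scale.* On the raw score it falls by about 7%.
- *That the SAP treats three visits as interchangeable.* Protocol 7.8.2.2 does not.
- *That every continuous measure should be averaged.* The expectation in SAP 7.3 concerns visual function. It is not stated for OCT/OCTA, autofluorescence or angiography.
- *That month 1 belongs in the average.* An effect expected within 3 months need not be complete at 1 month.
- *That a repeated-measures model would make multiple imputation largely unnecessary.* The documents give no missing-visit rate, and SAP 7.5 only says that imputation will be considered.

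**Conclusion.** The point holds as a modest, low-cost improvement. The SAP states an expected time course under which months 3 and 6 share one effect, and it plans no estimate that uses both.

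For change from baseline in acuity, averaging the two visits cuts variance by up to 25%. That is the precision of 10/0.75 = 13.3 eyes per arm instead of 10. The figure rests on the error SD of 6.2, independent visit errors, no patient-specific true change, complete visits, and an equal effect at both visits. Over the assumed ranges for correlated follow-up errors or varying true change, the cut is about 11% to 20%. The power figures depend on an assumed 10-letter effect and should not be read as the design's power.

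**What to change.** In SAP 7.3.1.1, add one supplementary exploratory contrast for visual acuity and microperimetry, and for ERG if the sponsor holds the same expectation there. It is the arm difference in mean change from baseline averaged over months 3 and 6, with a 95% CI.

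Estimate it in one of two ways:
- a repeated-measures model of change from baseline, with arm, visit, arm-by-visit and baseline value as covariate, allowing within-participant correlation; or
- a t-test on each participant's average change.

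State how baseline enters. A model of raw follow-up scores without baseline would keep only the 7% cut. Keep the protocol's month 6 comparison as the lead contrast and show month 1 as part of the time course.

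The cost is a paragraph of SAP text and a little programming, with no new visits or measurements. The downside is small but should be stated: the average understates an effect confined to one visit. On the change scale, under independent errors, it does worse than month 6 alone if the month 3 effect is below about 73% of the month 6 effect. Keeping the month 6 contrast covers that case.
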